**Table 8. Cohort Dose Stopping Rules**

Scenario	Action

Any occurrence of a CTCAE v4 Grade 3 or greater suspected adverse drug reaction or occurrence of an event (including but not limited to abnormalities in vital sign, ECG or clinical laboratory results) requiring complete withdrawal of IP administration in the same cohort.(Continued)
	
Otherwise, upon unanimous decision of the DLRM members, one of the following decisions may be made:
 
 
- Resume dosing of index subject(s) if applicable
 
- Resume enrollment of the cohort as planned
 
- Resume enrollment of the cohort at a lower dose
 
- Expand the cohort at the same dose
 
- Add a lower dose cohort to the study
 
- Escalate to the next planned dose
 
- Escalate to an intermediate dose (a dose lower than the next planned dose)
 

Confirmed QTc <math>\geq</math> 500 msec or prolonged to <math>\geq</math> 60 msec from baseline in 2 subjects in the cohort within the first 6 hours post dose
	
Dosing will be stopped for any subject that meets this criterion.
 
Serum potassium, magnesium and calcium will be measured immediately and the patient will receive supplementation to correct any low values. The investigator should notify the Amgen medical monitor immediately.
 
Electrocardiogram monitoring will continue hourly for at least 3 hours until the QTc interval decreases to < 480 msec. If hourly ECG's demonstrate a rising QTc interval or QTc prolongation >515 msec, the subject will continue to be monitored for at least 24 hours until the QTc decreases to < 480 msec.
 
A DLRM will be held to analyze all relevant safety and PK data (if available) and decide on the following options
 
 
- Resume dosing of index subject(s) (if applicable)
 
- Stop enrollment of the cohort
 
- Complete enrollment of the cohort at the same dose level
 
- Expand the cohort at the same dose level
 
- Open a new cohort at a lower dose level
 
- Escalate to an intermediate dose (a dose lower than the next planned dose)
 
- Escalate to the next planned dose level
 

Approved

Abbreviations: CTCAE = Common terminology Criteria for Adverse Events;  
a Finding must be confirmed by repeat measurement, whenever possible

## 6.2.2 Non-Amgen Investigational Product

Not applicable for this study.

## 6.3 Non-Investigational Product

Not applicable for this study.

### 6.3.1 Non-Amgen Non-Investigational Product

Not applicable for this study.

## 6.4 Other Protocol-required Therapies

Not applicable for this study.

## 6.5 Hepatotoxicity Stopping and Rechallenge Rules

Subjects with abnormal hepatic laboratory values (ie, alkaline phosphatase [ALP], aspartate aminotransferase [AST], alanine aminotransferase [ALT], total bilirubin [TBL]) and/or international normalized ratio [INR] and/or signs/symptoms of hepatitis (as described below) may meet the criteria for withholding or permanent discontinuation of Amgen investigational product or other protocol-required therapies as specified in the Guidance for Industry Drug-Induced Liver Injury: Premarketing Clinical Evaluation, July 2009).

### 6.5.1 Criteria for Permanent Discontinuation of Amgen Investigational Product and Other Protocol-required Therapies due to Potential Hepatotoxicity

Investigational product should be discontinued permanently and the subject should be followed according to the recommendations in [Appendix A](#) (Additional Safety Assessment Information) for possible drug-induced liver injury (DILI), if ALL of the criteria below are met:

- TBL > 2x upper limit of normal (ULN) or INR > 1.5
- AND increased AST or ALT from the relevant baseline value as specified below:

Baseline AST or ALT value	AST or ALT elevation
< ULN	> 3x ULN

- AND no other cause for the combination of the above laboratory abnormalities is immediately apparent; important alternative causes for elevated AST/ALT and/or TBL values include, but are not limited to:
  - Hepatobiliary tract disease
  - Viral hepatitis (eg, Hepatitis A/B/C/D/E, Epstein-Barr Virus, cytomegalovirus, Herpes Simplex Virus, Varicella, toxoplasmosis, and Parvovirus)
  - Right sided heart failure, hypotension or any cause of hypoxia to the liver causing ischemia.

Approved

- Exposure to hepatotoxic agents/drugs or hepatotoxins, including herbal and dietary supplements, plants and mushrooms
- Heritable disorders causing impaired glucuronidation (eg, Gilbert's Syndrome, Crigler-Najjar syndrome) and drugs that inhibit bilirubin glucuronidation (eg, indinavir, atazanavir)
- Alpha-one antitrypsin deficiency
- Alcoholic hepatitis
- Autoimmune hepatitis
- Wilson's disease and hemochromatosis
- Nonalcoholic Fatty Liver Disease including Steatohepatitis (NASH)
- Non-hepatic causes (eg, rhabdomyolysis, hemolysis)

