### 4.1 Inclusion Criteria

- 101 Subject has provided informed consent prior to initiation of any study-specific activities/procedures.
- 102 Male and female subjects  $\geq 18$  to  $\leq 55$  years old with no history or evidence of clinically relevant medical disorders as determined by the investigator and the Amgen physician (Parts A and B only)
- 103 Body mass index (BMI) between 18 and 35 kg/m^2, inclusive, at screening.
- 104 Physical examination including vital signs, clinical laboratory values, and ECGs are clinically acceptable to the investigator. Abnormal findings for healthy volunteers and unexpected findings for heart failure patient subjects will be discussed with Amgen prior to study enrollment.
- 105 Women must be of non-reproductive potential (ie, postmenopausal)
1. Age of  $\geq 55$  years with no menses for at least 12 months OR
  2. Age of  $< 55$  years with no menses for at least 12 months AND with postmenopausal gonadotropin levels (follicle-stimulating hormone levels  $> 40$  IU/L or according to the definition of “postmenopausal range” for the laboratory involved) OR
  3. History of hysterectomy OR
  4. History of bilateral oophorectomy.
- 106 Men must agree to practice an acceptable method of effective birth control while on study through 11 weeks after receiving the last dose of investigational product (AMG 986 or placebo). Acceptable methods of effective birth control include sexual abstinence; vasectomy and testing that shows there are no sperm in the semen; or a condom with spermicide (men) in combination with barrier methods (diaphragm, cervical cap or cervical sponge), hormonal birth control or IUS (women).

Approved

- 107 Men must be willing to abstain from sperm donation while on study through 11 weeks after receiving the last dose of investigational product (AMG 986 or placebo).
- 108 This inclusion criterion only applies to Parts B and C cohorts. Before inclusion in the study, subjects will undergo a screening echocardiogram to ensure that the following parameters can be accurately measured: left ventricular end-systolic and end-diastolic volumes, left atrial end-systolic and end-diastolic volumes, ejection fraction, fraction shortening, and end-systolic septal and posterior wall thickness.

For Part C

Additional Inclusion Criteria for HFrEF Patients

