**Table 8. Cohort Dose Stopping Rules**

Scenario	Action
Any occurrence of a single CTCAE v4 Grade 2 adverse drug reaction or higher in a cohort, or occurrence of an event (including but not limited to abnormalities in vital sign, ECG or clinical laboratory results) suspected of being caused by administration of IP.	Stop dosing index subjects and additional subjects and convene DLRM (if event occurs outside the regularly scheduled DLRM window)  Review adverse event and all relevant safety data for evidence of relationship to treatment and clinical or medical significance.  Treatment unblinding to support evaluation of safety a  Upon unanimous decision by the DLRM members, one of the following decisions may be made: 

- Resume dosing of index subject (if applicable)

- Stop enrollment of the cohort (if applicable)

- Resume enrollment of the cohort as planned

- Resume enrollment of the cohort at a lower dose

- Expand the cohort at the same dose

- Add a lower dose cohort to the study

- Escalate to an intermediate dose (a dose lower than the next planned dose)

- Escalate to the next planned dose

Abbreviations: CTCAE = Common terminology Criteria for Adverse Events;

a Finding must be confirmed by repeat measurement, whenever possible

Page 1 of 3

Approved

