**Table 8. Cohort Dose Stopping Rules**

Scenario	Action

Any occurrence of a CTCAE v4 Grade 2 suspected adverse drug reaction in 2 or more subjects in the same cohort, or occurrence of two events (including but not limited to abnormalities in vital sign, ECG or clinical laboratory results) requiring reduction in the dose administered in the same cohort.
	
Stop dosing index subjects and additional subjects and convene DLRM (if event occurs outside the regularly scheduled DLRM window)
 
Review adverse event and all relevant safety data for evidence of relationship to treatment and clinical or medical significance.
 
Treatment unblinding to support evaluation of safetya
 
Upon unanimous decision by the DLRM members, one of the following decisions may be made:
 
 
- Resume dosing of index subject (if applicable)
 
- Stop enrollment of the cohort (if applicable)
 
- Resume enrollment of the cohort as planned
 
- Resume enrollment of the cohort at a lower dose
 
- Expand the cohort at the same dose
 
- Add a lower dose cohort to the study
 
- Escalate to an intermediate dose (a dose lower than the next planned dose)
 
- Escalate to the next planned dose
 

Any occurrence of a CTCAE v4 Grade 3 or greater suspected adverse drug reaction or occurrence of an event (including but not limited to abnormalities in vital sign, ECG or clinical laboratory results) requiring complete withdrawal of IP administration in the same cohort.
	
Stop dosing index individual and additional subjects in the cohort and convene DLRM (if event occurs outside regularly scheduled DLRM window)
 
Review adverse event and all relevant safety data for evidence of relationship to treatment and clinical or medical significance
 
Treatment unblinding to support evaluation of safetya
 
If an adverse event is determined by unanimous decision of the DLRM members to be related to investigational product and clinically or medically significant, no further doses should be administered at this dose and no dose escalation should proceed. Enrollment of the study may continue at a lower dose or a lower dose cohort may be added to the study

Approved

Abbreviations: CTCAE = Common terminology Criteria for Adverse Events;  
a Finding must be confirmed by repeat measurement, whenever possible

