### 6.5.2 Criteria for Conditional Withholding of Amgen Investigational Product and Other Protocol-required Therapies due to Potential Hepatotoxicity

For subjects who do not meet the criteria for permanent discontinuation of Amgen investigational product outlined above and have no underlying liver disease, and eligibility criteria requiring normal transaminases and TBL at baseline or subjects with underlying liver disease and baseline abnormal transaminases, the following rules are recommended for withholding of Amgen investigational product and other protocol-required therapies:

- Elevation of either AST or ALT according to the following schedule:

Baseline AST or ALT value	AST or ALT elevation
Any	> 8x ULN at any time
Any	> 5x ULN but < 8x ULN for $\geq 2$ weeks
Any	> 5x ULN but < 8x ULN and unable to adhere to enhanced monitoring schedule
Any	> 3x ULN with clinical signs or symptoms that are consistent with hepatitis (such as right upper quadrant pain/tenderness, fever, nausea, vomiting, jaundice).

- OR: TBL > 3x ULN at any time
- OR: ALP > 8x ULN at any time

Investigational product should be withheld pending investigation into alternative causes of DILI. If investigational product is withheld, the subject is to be followed according to recommendations in [Appendix A](#) for possible DILI. Re-challenge may be considered if an alternative cause for impaired liver tests (ALT, AST, ALP) and/or elevated TBL, is discovered and the laboratory abnormalities resolve to normal or baseline ([Section 6.5.3](#)).

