### **6.5.3 Criteria for Re-challenge of Amgen Investigational Product and Other Protocol-required Therapies After Potential Hepatotoxicity**

The decision to re-challenge the subject should be discussed and agreed upon unanimously by the subject, investigator, and Amgen.

If signs or symptoms recur with re-challenge, then Amgen investigational product and other protocol-required therapies, as appropriate should be permanently discontinued. Subjects who clearly meet the criteria for permanent discontinuation (as described in [Section 6.5.1](#)) should never be re-challenged.

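### A subject admitted with baseline AST/ALT at or above ULN can never meet the Section 6.5.1 permanent-discontinuation rule, because its table has a row only for baseline below ULN

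*Protocol*

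**What the plan says.** **Entry (Protocol 4.1, 4.2).** No criterion gives a number for AST, ALT or TBL. Criterion 104 leaves laboratory values to the investigator's judgement; in Part C, "unexpected findings for heart failure patient subjects will be discussed with Amgen prior to study enrollment". Criterion 207 covers viral serology only. Criteria 102 (Parts A and B) and 210 (all parts) are also judgements.

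**Permanent stop (6.5.1).** All three conditions must hold: TBL above 2x ULN or INR above 1.5; "AND increased AST or ALT from the relevant baseline value as specified below", with one table row (baseline below ULN, elevation above 3x ULN); and no other cause immediately apparent.

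**Conditional withholding (6.5.2).** The scope sentence refers to "eligibility criteria requiring normal transaminases and TBL at baseline or subjects with underlying liver disease and baseline abnormal transaminases". The rows apply to any baseline: above 8x ULN; between 5x and 8x for two weeks or more, or with enhanced monitoring not possible; above 3x with signs or symptoms of hepatitis. TBL above 3x ULN or ALP above 8x ULN also qualifies. There is no INR line. Afterwards, "Re-challenge may be considered if an alternative cause for impaired liver tests (ALT, AST, ALP) and/or elevated TBL, is discovered" and the abnormalities resolve.

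**Re-challenge (6.5.3).** "The decision to re-challenge the subject should be discussed and agreed upon unanimously by the subject, investigator, and Amgen". Recurrence of signs or symptoms on re-challenge means permanent discontinuation. Only one group may never be re-challenged: "Subjects who clearly meet the criteria for permanent discontinuation".

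**The concern.** The wording of 6.5.1 promises a limit that depends on baseline, and then supplies one baseline stratum. Section 6.5.2 shows that abnormal baseline transaminases were foreseen, yet it also relies on eligibility criteria requiring normal values, and Section 4 contains none. The two sections do not fit together, and the subject who falls between them is one the protocol admits.

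Take two Part C patients with the same on-treatment liver picture and no other cause apparent. The one with normal baseline is to be stopped permanently and never re-challenged. The one slightly above ULN depends on withholding rules with higher limits, or on a judgement that the change is drug-related. Safety in heart failure patients is a primary objective. The point matters for repeat dosing in Parts B and C; with a single dose, as in the Part A oral cohorts, permanent discontinuation changes little.

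**Working it through.** **Inputs.** The limits are those in 6.5.1 and 6.5.2. Part C dosing ends on Day 21 (3.1), and 30 Part C patients receive AMG 986 (10.2). Values are multiples of ULN. Baseline means that of the enzyme that rises; a subject with only one raised enzyme could still meet the row through the other. Section 6.5.2 is read generously, so that its any-baseline rows cover everyone. ALP is normal, enhanced monitoring is feasible and no other cause is apparent.

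**Rules as logic.**
- 6.5.1 = (TBL > 2 or INR > 1.5) and (baseline < 1 and ALT > 3).
- 6.5.2 = ALT > 8, or (5 < ALT < 8 for 2 weeks or more), or (ALT > 3 with symptoms), or TBL > 3.

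At baseline 1 or higher the second bracket of 6.5.1 is false whatever ALT does.

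**Worked cases, asymptomatic.**

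| On treatment | Baseline 0.9x | Baseline 1.2x |
|---|---|---|
| ALT 4, TBL 2.5 | 6.5.1 met | no Section 6.5 rule met |
| ALT 4, INR 1.8, TBL 1.5 | 6.5.1 met | no Section 6.5 rule met |
| ALT 7, TBL 2.5, first seen Day 8 | 6.5.1 met on Day 8 | none during dosing: 8 + 14 = Day 22, last dose Day 21 |
| ALT 9, TBL 2.5 | 6.5.1 met | withheld under 6.5.2; re-challenge possible |

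INR is not in Table 16, so in the second case it would come from the Appendix A repeat test. An elevation first seen on Day 2 reaches two weeks on Day 16, within dosing.

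**Grid.** ALT 3.5, 4.5, 6, 7.5, 9; TBL/INR 2.5/1.0, 1.5/1.8, 3.5/1.0; symptoms no/yes; two weeks reached no/yes where ALT is 5 to 8. Cells: 3 ALT levels x 3 x 2 = 18, plus 2 ALT levels x 3 x 2 x 2 = 24; total 42. All 42 satisfy the on-treatment limits of 6.5.1 by construction.
- Baseline 0.9x: 6.5.1 met in 42.
- Baseline 1.2x: 6.5.1 met in 0; 6.5.2 met in 34; neither in 42 - 34 = 8. The 8 are ALT 3.5, 4.5, 6 and 7.5, each with 2.5/1.0 and 1.5/1.8, without symptoms and under two weeks.

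A separate set of seven patterns agrees: 6.5.1 is met in 7 of 7 at baseline 0.8x and in 0 of 7 at 1.0x and 1.5x, where 6.5.2 is met in 3 and neither in 4.

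**Patients.** The share with raised baseline is not given. Assume 5% to 20%: 30 x 0.05 = 1.5 to 30 x 0.20 = 6 patients to whom 6.5.1 cannot apply. Assume also that 0.5% to 2% of them reach the on-treatment limits: 1.5 x 0.005 = 0.0075 to 6 x 0.02 = 0.12. Section 2.4.1 reports 8 heart failure patients already treated by June 2018; for the other 22 the range is 0.0055 to 0.088.

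**Candidate new row.** Limit = max(3, m x baseline).

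| m | baseline 1.2x | 2.0x | 2.9x |
|---|---|---|---|
| 1.5 | 3 | 3 | 4.35 |
| 2 | 3 | 4 | 5.8 |
| 3 | 3.6 | 6 | 8.7 |

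With m = 2 the limit stays at 3x ULN for baselines up to 3/2 = 1.5x. Of the 8 open cells it closes 8 at baseline 1.2x, 6 at 2.0x (both ALT 3.5 cells remain) and 4 at 2.9x (the ALT 3.5 and 4.5 cells remain).

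**The case against.** A reader might infer that a subject with raised baseline has no permanent-discontinuation rule at all, or is unprotected. The documents do not support that. At any baseline:
- 6.5.2 withholding applies, on the generous reading, and 6.5.3 requires a permanent stop if signs or symptoms recur on re-challenge.
- Section 6.2.1.3.3 has an individual scheme for Part C covering significant laboratory changes judged directly related to oral dosing; product can be withheld, reduced or resumed by agreement.
- Table 8 responds to a suspected drug-related laboratory event with "Stop dosing index subjects and additional subjects and convene DLRM". After a Grade 3 or higher event judged related and significant, "no further doses should be administered at this dose and no dose escalation should proceed".
- Grade 2 or higher adverse events reach an unblinded medical monitor, with review within 24 hours (6.2.1.3.1, 9.2.2.1).
- Appendix A requires close observation above 3x ULN, with repeat tests within 24 hours.

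Nor should a reader infer that such an event would go unreported. Appendix A requires other hepatotoxicity events to be reported as SAEs where they meet the SAE criteria, and Section 9.1.3 names DILI as an example of a medically important event.

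Two further objections have force. The no-other-cause condition in 6.5.1 may often fail in heart failure, since right-sided heart failure and hypotension are listed causes; a new row would not help there. And 42 against 0 restates the table and says nothing about how often the problem arises.

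All of this limits the size of the point. It does not remove it. Table 8 and the Part C scheme need a judgement of drug-relatedness, and the DLRM may resume dosing in most Table 8 scenarios. Close observation monitors without stopping dosing. The numeric trigger in 6.5.1 is still out of reach for these subjects.

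**Conclusion.** The point holds as a minor safety-rule correction. Followed as written, the primary laboratory-based permanent-discontinuation rule, and the absolute re-challenge bar tied to it, cannot apply to a subject admitted at or above ULN. The 6.5.2 scope sentence cites entry criteria that do not exist.

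The zone covered by no Section 6.5 rule is narrow: asymptomatic, able to follow monitoring, AST/ALT above 3x and up to 8x ULN (under two weeks if above 5x), with TBL above 2x and up to 3x ULN, or INR above 1.5 with TBL no higher than 3x, and no other cause immediately apparent. Expected cases are well below one, on rates that are assumptions.

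The conclusion rests on the 6.5.1 table having one row. A row lost in text extraction cannot be excluded, although the neighbouring 6.5.2 table came through with four. The external guidance cited in 6.5 was not available.

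**What to change.** 1. Add a row to the 6.5.1 table for baseline AST/ALT at or above ULN: above 3x ULN together with a stated rise over baseline. The sponsor's safety lead should set the multiple. Twice baseline is one option. It avoids triggering on a drift from 2.9x to 3.1x ULN, but it closes the whole zone only for baselines up to 1.5x ULN and part of it above that.
2. End the 6.5.2 scope sentence after its first condition, so that it covers every subject who does not meet 6.5.1, with no reference to entry criteria or underlying liver disease.

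The 6.5.3 bar then follows for subjects who meet the new row. No new entry criterion or data are needed: chemistry is already taken at screening and Day -1, and Appendix A already calls for INR.

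The cost is one row and one shortened sentence in an amendment, and possibly a few more permanent discontinuations among subjects with raised baseline enzymes. The SAP's version history records that the study was discontinued early, so the practical use now is in any later protocol that carries this section over.

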### 6.5.2 Criteria for Conditional Withholding of Amgen Investigational Product and Other Protocol-required Therapies due to Potential Hepatotoxicity

For subjects who do not meet the criteria for permanent discontinuation of Amgen investigational product outlined above and have no underlying liver disease, and eligibility criteria requiring normal transaminases and TBL at baseline or subjects with underlying liver disease and baseline abnormal transaminases, the following rules are recommended for withholding of Amgen investigational product and other protocol-required therapies:

- Elevation of either AST or ALT according to the following schedule:

Baseline AST or ALT value	AST or ALT elevation
Any	> 8x ULN at any time
Any	> 5x ULN but < 8x ULN for $\geq 2$ weeks
Any	> 5x ULN but < 8x ULN and unable to adhere to enhanced monitoring schedule
Any	> 3x ULN with clinical signs or symptoms that are consistent with hepatitis (such as right upper quadrant pain/tenderness, fever, nausea, vomiting, jaundice).

- OR: TBL > 3x ULN at any time
- OR: ALP > 8x ULN at any time

Investigational product should be withheld pending investigation into alternative causes of DILI. If investigational product is withheld, the subject is to be followed according to recommendations in [Appendix A](#) for possible DILI. Re-challenge may be considered if an alternative cause for impaired liver tests (ALT, AST, ALP) and/or elevated TBL, is discovered and the laboratory abnormalities resolve to normal or baseline ([Section 6.5.3](#)).

### **6.5.3 Criteria for Re-challenge of Amgen Investigational Product and Other Protocol-required Therapies After Potential Hepatotoxicity**

The decision to re-challenge the subject should be discussed and agreed upon unanimously by the subject, investigator, and Amgen.

If signs or symptoms recur with re-challenge, then Amgen investigational product and other protocol-required therapies, as appropriate should be permanently discontinued. Subjects who clearly meet the criteria for permanent discontinuation (as described in [Section 6.5.1](#)) should never be re-challenged.

